4.2. Efficacy Variables

The clinical efficacy will be evaluated by investigator per RECIST (Response Evaluation Criteria in Solid Tumors) 1.1. The efficacy variables including:

- Best overall response (BOR) is defined as the best overall response recorded from the start of treatment until disease progression or the last tumor assessment, whichever occurs earlier.
- Overall response rate (ORR) is defined as the proportion of subjects with BOR of complete response (CR) or partial response (PR).
- Disease control rate (DCR) is defined as the proportion of subjects with a BOR of CR, PR, or stable disease (SD).
- Duration of response (DOR) is defined as the time from first evidence of CR or PR to disease progression or death from any cause, whichever occurs first.

- Progression free survival (PFS) is defined as the time from start of study treatment until disease progression or death from any cause, whichever occurs first.
- Time to progression (TTP) is defined as the time from start of study treatment until disease progression.

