8. STATISTICAL METHOD

8.1. General Statistical Consideration

The statistical analysis plan be finalized prior to data base lock. All analyses and data presentations will be generated using SAS® Version 9.4 or higher software

Descriptive summary

Continuous variables: Descriptive statistics will include the number of non-missing values (n), arithmetic mean, standard deviation (SD), median, minimum and maximum values.

The minimum and maximum values will be displayed to the same decimal precision as the source data, the arithmetic mean and median values will be displayed to one more decimal than the source data, and the SD value will be displayed to two more decimals than the source data for the specific variable.

Categorical variables: Descriptive statistics will include counts and percentages per category. The denominator in all percentage calculations will be the number of participants in the relevant analysis set, unless otherwise specified. Percentages will be displayed to one decimal place with the following exceptions: 1) percentages will not be displayed for zero frequencies; 2) percentages will be displayed as "100%" when percentage is 100%.

ORR and DCR will be calculated, the corresponding two-sided 90% confidence intervals will be estimated by the Clopper-Pearson method.

Baseline

Baseline is defined as the last non-missing measurement collected on or before first study drug administration. For ECGs, the average of the ECG parameters should be used.

Censor rule

Table 3 below shows the censor rule for PFS:

Table 3 Censor rule for PFS

No.	Situation	Event or Censor / Analyais date
1	PD or death	Event / PD date or death date
2	Have at least one post-baseline assessment, no PD, no Death	Censor / Last imaging date
3	No post-baseline assessment and no Death	Censo r/ First dosing date

Only subjects with the BOR of CR or PR will be included for DOR analysis. DOR will apply the same consor rule as PFS.

Best overall response (BOR) is the best measured response at any time post treatment. Subject without any post-treatment assessments will be treated as non-responder.

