8.2. Subjects in Study

8.2.1. Subjects Dispostion

From screening to study completion, the following summaries will be provided:

- Summary of the number of patients who screen success for entry into the study and screen failure, respectively, and the number of subjects treated with at least 1 dose of GFH018 (All enrolled population)
- Summary of the number and percentage of treatment withdraws by primary reason and overall (full analysis set) and the number and percentage of study discontinuation by primary reason and overall (full analysis set).

A by-subject listing of reasons for screen failure reason(s), treatment discontinuation, study discontinuation with date and reasons for discontinuation.

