8.5. Efficacy Analysis

Efficacy analyses will be performed for subjects in the FAS based on RECIST evaluation.

A waterfall plot will be presented for the best percentage change from baseline in the sum of target lesion diameters. Swim plots will be prepared for all subjects to present subject drug exposure and efficacy evaluations at each visit.

The best overall response (BOR) will be determined and statistically analyzed based on evaluations at all visit, and the number and percentage of subjects with BOR of CR, PR, SD, PD, NE, and Non-CR/Non-PD will be summarized. Participants with BOR of unknown or none (i.e. no valid record of post-baseline tumor assessments) will be considered non-responsive. ORR (CR or PR) and DCR (CR, PR or SD) will be calculated based on BOR, respectively, and the Clopper-pearson method will be used to estimate ORR and DCR and their 2-sided 90% confidence intervals.

Time to progression (TTP), duration of response (DOR), and progression-free survival (PFS) will be analyzed using the Kaplan-Meier method, with their median and 90% confidence interval will be provided. If the number of subjects in a group is less than 10, only DOR, TTP and PFS listings will be provided for each subject.

Assessments of target lesion, non-target lesion, new lesion, and overall response will be listed in detail for each subject and each visit.

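### The best overall response rules do not stop at the start of a new anti-cancer therapy, so a response under a later treatment would count towards GFH018's ORR and DCR

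*SAP*

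**What the plan says.** The SAP describes best overall response in three places:

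- Section 4.2 defines it as the "best overall response recorded from the start of treatment until disease progression or the last tumor assessment, whichever occurs earlier".
- Section 8.1 says "Best overall response (BOR) is the best measured response at any time post treatment".
- Section 8.5 says that BOR "will be determined and statistically analyzed based on evaluations at all visit".

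ORR and DCR are calculated from BOR. The waterfall plot in 8.5 uses the best percentage change in the sum of target lesion diameters and states no end to its window.

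For PFS, section 4.2 reads "Progression free survival (PFS) is defined as the time from start of study treatment until disease progression or death from any cause, whichever occurs first". Table 3 in section 8.1 has three rows:

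- Progression or death: "Event / PD date or death date".
- "Have at least one post-baseline assessment, no PD, no Death": censored at the date of the last imaging.
- "No post-baseline assessment and no Death": censored at the first dosing date.

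DOR takes the PFS rule. No censoring rule is given for TTP.

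Anti-tumor therapy appears only as prior therapy (8.2.5). Other drugs appear only as prior or concomitant medication (8.2.6), with starts counted up to 30 days after the last dose. Neither section is linked to an efficacy rule.

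**The concern.** Section 8.2.1 lists "treatment discontinuation, study discontinuation with date and reasons for discontinuation", so stopping GFH018 and leaving the study are separate events. Section 8.4.1 provides for adverse events that lead to treatment discontinuation. A subject can therefore be off GFH018 without having progressed. If that subject starts another therapy and is scanned again, the BOR window is still open.

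The trial is open-label and non-randomized, so its ORR, DCR and waterfall plot will be read as the activity of GFH018. Preliminary antitumor efficacy is one of several inputs to the RDE (section 3), and efficacy seen in escalation is one basis for choosing the expansion tumor types. In groups this small, one response attributed to the wrong drug changes the impression a reader takes away.

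**Working it through.** **Step 1: the BOR rules side by side.** Section 4.2 ends the window at the earlier of progression and the last assessment. Section 8.1, read as any time after treatment start, does not stop even at progression. Section 8.5 uses every visit. The three wordings differ on progression, but none stops at new therapy.

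**Step 2: follow one subject.** Suppose the best response on GFH018 is SD, the subject stops for an adverse event, starts another therapy, and a later scan shows PR with no progression in between.

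- Under 4.2 there is no progression, so the window runs to the last assessment and BOR is PR.
- Under 8.1 and 8.5, BOR is also PR.
- The subject counts in the ORR numerator, and the later shrinkage enters the waterfall plot.
- Because BOR is PR, the subject also enters the DOR analysis, with DOR starting at a scan made under the other therapy.

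If instead the first evaluable post-baseline scan falls after the switch and shows SD, the subject counts in DCR.

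**Step 3: are the Table 3 rows exhaustive?** They cover progression or death; assessed with neither; and not assessed and alive. Every subject falls into one row, so the SAP assigns an outcome to the subject who switches: an event on its own date, or censoring at the last imaging. That last scan may have been made under the new therapy. It may also be non-evaluable, although 8.5 recognises NE as a category.

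**Step 4: size for ORR.** The SAP gives no figure to reproduce. Inputs are the two-sided 90% Clopper-Pearson interval (8.1, 8.5) and 6 to 12 subjects per treatment in expansion, with at least 12 at the RP2D (section 6). Escalation cohorts are 3 to 6, so n = 6 is also the top of that range.

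With x responders among n:

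- lower limit = BetaInv(0.05; x, n − x + 1), which is 0 when x = 0 and 1 − 0.95^(1/n) when x = 1
- upper limit = BetaInv(0.95; x + 1, n − x), which is 1 − 0.05^(1/n) when x = 0

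| n | Later-therapy PR excluded | Later-therapy PR counted |
|---|---|---|
| 6 | 0/6 = 0%; upper 1 − 0.05^(1/6) = 39.3% | 1/6 = 16.7%; lower 1 − 0.95^(1/6) = 0.9%; upper BetaInv(0.95; 2, 5) = 58.2% |
| 12 | 0/12 = 0%; upper 1 − 0.05^(1/12) = 22.1% | 1/12 = 8.3%; lower 1 − 0.95^(1/12) = 0.4%; upper BetaInv(0.95; 2, 11) = 33.9% |

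The upper limit rises by 58.2 − 39.3 = 18.9 points at n = 6 and by 33.9 − 22.1 = 11.8 points at n = 12. The table assumes exactly one such response and no other responder.

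**The case against.** **The scenario may be rare or impossible.** Section 8.2.1 separates treatment and study discontinuation but says nothing about tumor imaging after treatment. The only follow-up length in the SAP is 30 days (± 3 days), given for adverse events in 4.1.1. If imaging also ended then, a subject would have to stop without progression, start another therapy and reach a first PR in about a month. The protocol, not at hand here, may also end assessments at new therapy. This stands as a limit on frequency. It does not change what the SAP's own rules do with such a scan.

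**It would not be hidden.** A reader might infer that nothing in the outputs could expose a misattributed response. The documents do not support that. Section 8.5 plans swim plots of exposure and evaluations for all subjects, with per-visit response listings, and 8.3 lists first and last dose dates. A response after the last dose could be noticed, but the ORR, DCR and waterfall results would still contain it.

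**PFS and DOR follow their definitions.** A reader might infer that counting progression or death under a later therapy is an error. It is not shown to be one. The first row of Table 3 implements the stated PFS definition, and counting events whatever therapy follows is a recognised treatment-policy choice. Censoring at new therapy can itself be informative. What stands is that the SAP does not declare the choice.

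**Decisions and cohort sizes.** A reader might take the 12-subject figures as the effect on the RDE decision. That decision uses escalation cohorts of 3 to 6 and also weighs safety, PK and pharmacodynamics. The 12-subject figures apply to the RP2D cohort.

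**Conclusion.** The concern holds for BOR and everything derived from it. Read literally, sections 4.2, 8.1 and 8.5 count a CR or PR reached under a later therapy in ORR and DCR, a first SD in DCR, and further shrinkage in the waterfall plot. This is the effect of rules that the SAP itself states, not a detail left to the protocol.

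Each such response adds 16.7 points to ORR at n = 6 or 8.3 points at n = 12. This rests on the assumption that at least one subject stops without progression, starts other therapy and is scanned again; the SAP gives no basis for a frequency. It would be going too far to say that such responses will occur or be credited in this trial.

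For PFS and DOR the finding is narrower: an undeclared strategy, whose effect on the estimates could go in either direction. TTP has no censoring rule at all. Censoring at a possibly non-evaluable last scan is a separate, smaller defect that does not depend on new therapy.

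Efficacy is descriptive and section 5 states that no hypothesis is tested, so no error rate is affected. The change is worth making before database lock because it is cheap and bears on the main activity figures.

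**What to change.** 1. **BOR.** Use one wording in 4.2, 8.1 and 8.5: *BOR, ORR, DCR and best percentage change from baseline use only tumor assessments on or before the earlier of disease progression and the start of any new anti-cancer therapy.* This also reconciles the three present wordings.
2. **Table 3, second row.** Replace the date of the last imaging with the date of the last evaluable (not NE) tumor assessment.
3. **PFS, DOR and TTP.** State whether events after new therapy count (treatment policy, as Table 3 now implies) or are censored at the last evaluable assessment before it. Show the other approach as a sensitivity display where Kaplan-Meier estimates are produced. Section 8.5 gives listings only for groups below 10, so this affects groups of at least 10. State the censoring rule for TTP explicitly.

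The cost is a few sentences and one table cell. Slightly fewer assessments will count. The start date of new anti-cancer therapy is needed, and the medication definitions in 8.2.6 cover it only to 30 days after the last dose. If imaging continues beyond that, the SAP must name another source for the date.

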4.3. Pharmacodynamic Biomarkers

Pharmacodynamic biomarkers includes TGF-β and pSMAD2/3.

4.4. Pharmacokinetic Parameters

Single-dose paremeters include: Cmax, Tmax, AUC_{0-12h} , AUC_{0-24h} , AUC_{0-inf} , $T_{1/2}$, CL/F, Vd/F. Steady-state parameters include: $C_{max,ss}$, $C_{min,ss}$, $T_{max,ss}$, AUC_{tau} , $T_{1/2}$, CL/F, Vd/F, CLr, Racc.

5. STATISTICAL HYPOTHESIS

No statistical hypothesis will be tested in this study.

6. SAMPLE SIZE

Dose escalation part:

Subjects will be enrolled and treated in cohort of size 3-6. Approximately 20-40 subjects are planned to be enrolled. Additional subjects may be enrolled if more dose levels or alternative dosing regimens are to be explored.

Dose expansion part:

6-12 subjects are planned to be enrolled in each treatment. A minimum of 12 subjects should be included in the cohort of RP2D (subjects who have received the same treatment regimen will be counted).

7. ANALYSIS DATASETS

7.1. Screening Set

Screening set: consists of subjects who signed the informed consent.

7.2. Full Analysis Set (FAS)

FAS: consists of all subjects who have received at least one dose of study treatment.

7.3. Safety Set (SS)

SS: consists of all subjects who have received at least one dose of study treatment and had at least one valid post-baseline safety assessment.

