7.5. Dose-determining Set (DDS)

DDS: consists of all subjects who have received at least 80% of the total planned dose of GFH018, are considered to have sufficient safety evaluation during the 31-day-observation period or developed DLT during the first cycle.

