8.4. Safety Analysis

All safety analyses will be based on the safety set (SS), except for the DLT analysis which will be based on the dose-determining set (DDS). Baseline definition for safety analyses are provided in Section 8.1.

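### The Safety Set requires an undefined valid post-baseline safety assessment, so the safety and exposure summaries can lose a treated subject who dies or leaves early

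*SAP*

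**What the plan says.** - **Safety Set (SAP 7.3).** There are two conditions. The first is treatment: "SS: consists of all subjects who have received at least one dose of study treatment". The second is that the subject "had at least one valid post-baseline safety assessment". The section gives no rule for what makes an assessment valid and no cross-reference to one.
- **Full Analysis Set (SAP 7.2).** Treatment is the only condition: "FAS: consists of all subjects who have received at least one dose of study treatment".
- **Use of the SS (SAP 8.4).** "All safety analyses will be based on the safety set (SS"), with one exception: "except for the DLT analysis which will be based on the dose-determining set (DDS"). Section 8.4.1 then lists the TEAE, SAE, AESI and cause-of-death summaries. Section 8.3 places cumulative dose, duration of exposure, dose intensity and compliance on the SS as well.
- **Dose-determining set (SAP 7.5).** A subject who "or developed DLT during the first cycle" is admitted. The other route requires the subject to have "received at least 80% of the total planned dose of GFH018" together with sufficient safety evaluation.
- **Disposition (SAP 8.2.1).** Withdrawals from treatment and from the study, by reason, are tabulated on the FAS.
- **Denominators (SAP 8.1).** Percentages are taken over the size of the relevant analysis set unless otherwise specified.

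**The concern.** Safety and tolerability are a primary objective (SAP section 2), yet membership of the set that carries most of the safety output depends on something observed after treatment starts. Early death, or withdrawal because of toxicity, can prevent that observation. A subject left out leaves both numerator and denominator, and with 3 to 6 subjects per cohort (SAP section 6) one subject changes the reported rate materially.

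The word valid adds discretion. The trial is open-label, so whoever decides whether an assessment is valid may know the dose and the outcome.

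The condition also fits poorly with the rest of the SAP. Efficacy is analysed on the FAS, and subjects without a post-baseline tumour assessment are kept as non-responders (sections 8.1 and 8.5). An adverse event whose timing is unclear is counted as treatment-emergent (section 4.1.1). Both rules are conservative, whereas the SS definition removes subjects for want of an observation.

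**Working it through.** The SAP gives no figure on this point, so there is none to reproduce. The check compares the definitions and then works out what one exclusion does.

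**Step 1: which outputs depend on the condition**

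| Output | Set | Can the SS condition remove a treated subject? |
|---|---|---|
| TEAE, SAE, AESI and cause-of-death summaries (8.4.1) | SS | Yes |
| Exposure and compliance (8.3) | SS | Yes |
| DLT analysis (8.4) | DDS | No |
| Disposition (8.2.1) | FAS | No |
| AE listings (8.4.1) | All AEs; no separate population named | Not settled by the text |

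**Step 2: effect of one exclusion on a rate**

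Let x of n treated subjects have the event. The all-treated rate is x/n.

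- If the excluded subject had the event, the rate becomes (x − 1)/(n − 1), a fall of (n − x)/[n(n − 1)].
- If the excluded subject did not, the rate becomes x/(n − 1), a rise of x/[n(n − 1)].

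Cohort sizes of 3 and 6 and the RP2D minimum of 12 come from SAP section 6. The event counts are illustrative.

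| All treated | Event subject excluded | Event-free subject excluded |
|---|---|---|
| 1/3 = 33.3% | 0/2 = 0% | 1/2 = 50.0% |
| 1/6 = 16.7% | 0/5 = 0% | 1/5 = 20.0% |
| 2/6 = 33.3% | 1/5 = 20.0% | 2/5 = 40.0% |
| 1/12 = 8.3% | 0/11 = 0% | 1/11 = 9.1% |

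Check for x = 1, n = 6: the fall is 5/30 = 16.7 percentage points and the rise is 1/30 = 3.3 points.

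**Step 3: how the reading of valid decides the direction**

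- If a reported adverse event or death counts as a valid assessment, subjects with a recorded event stay in. Only event-free subjects can be excluded, and rates can only rise.
- If only a scheduled examination or test counts, a subject with a recorded early event can be excluded, and the rate can fall, to zero in the single-event cases above.

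The SAP does not choose between these readings.

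**Step 4: how often an exclusion might occur**

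The SAP gives no frequency. As an assumption only, let each treated subject be excluded independently with probability q. Then P(at least one excluded) = 1 − (1 − q)^n. The sizes 20 and 40 are the planned range for the escalation part.

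| q (assumed) | n = 3 | n = 6 | n = 20 | n = 40 |
|---|---|---|---|---|
| 1% | 3.0% | 5.9% | 18.2% | 33.1% |
| 2% | 5.9% | 11.4% | 33.2% | 55.4% |
| 5% | 14.3% | 26.5% | 64.2% | 87.1% |
| 10% | 27.1% | 46.9% | 87.8% | 98.5% |

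For example, with q = 1% and n = 6: 1 − 0.99^6 = 5.9%. With q = 0 every entry is zero.

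**The case against.** The best defence has four parts.

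1. **The lost-event case needs a narrow reading.** For 1/6 to become 0/5, the event must have been recorded while the subject has no valid post-baseline safety assessment. Section 4.1 lists adverse events first among the safety variables and collects them from consent through follow-up, so a recorded event may naturally count as an assessment. This is a fair point, and it makes the downward shift conditional. It does not clear the definition: the SAP never says that an event or death qualifies, and under that reading the condition removes only event-free subjects and inflates the rates.
2. **Exclusion is unlikely.** In the escalation part subjects have serial PK sampling for up to 72 hours after the first dose, so a treated subject with no post-dose contact should be rare. This limits the expected size. It does not show what the condition is for.
3. **Dose decisions do not rest on the SS.** The safety monitoring committee reviews DLTs, other adverse events of grade 2 and above, and PK and pharmacodynamic data. The MTD is defined by DLT incidence, which is analysed on the DDS. No hypothesis is tested. All of this stands, so the effect is confined to descriptive summaries.
4. **The protocol may define the set or the term.** It is not at hand, so this cannot be excluded. Section 7.3 does not refer to it, although the SAP does so for other definitions.

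A reader might infer that an early death can vanish from every safety table. The SAP does not support that: a first-cycle DLT enters the DDS whatever its SS status, discontinuations remain in the FAS disposition table, and the adverse event listings are meant to cover all events. The DDS is only a partial safeguard, because an early death or dropout not classed as a DLT does not clearly meet its dose criterion. A reader might also infer that the bias can only be downward. The event-free column in the working shows otherwise.

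**Conclusion.** The point holds in a limited form. The SS can be smaller than the all-treated FAS because of a condition that uses an undefined term and serves no stated purpose. Where it excludes anyone, it distorts the SS-based safety and exposure summaries, and the direction depends on whether the excluded subject had an event. With one event in the cohort, one exclusion moves 1/6 to 0/5 or to 1/5, and 1/3 to 0/2 or to 1/2. These figures assume that exactly one treated subject is excluded. How often that would happen cannot be derived from the SAP, and if every treated subject is assessed nothing changes. The DLT analysis, and with it the MTD definition, is not touched.

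**What to change.** In SAP section 7.3, delete the post-baseline assessment condition and define the SS exactly as the FAS is defined, as the set that "consists of all subjects who have received at least one dose of study treatment". Sections 8.3 and 8.4 can keep their references to the SS. By-visit tables continue to use the data available at each visit, so no separate population rule is needed for them.

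If the sponsor prefers to keep the condition, the minimum is to define a valid assessment and to state that any reported adverse event or death qualifies. That protects the numerator but still allows event-free subjects to drop out of the denominator, so the all-treated definition is better.

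The cost is a change of SAP wording before database lock. No additional data are needed, and if no treated subject would have been excluded, no result changes.
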